11.1.4. Safety variables

All safety variables except for the first safety endpoint "time to wound closure" will be evaluated on the safety set.

11.1.4.1. Safety Endpoint: Time to wound closure

This safety endpoint will be analyzed using the FAS. A sensitivity analysis will be done by repeating the analysis outlined below with the PP as analysis population.

Time to reach complete wound closure will be compared between the NexoBrid and SOC at a wound level using a method of survival analysis with clustered data that is based on appropriate assumptions. By "clustered data", we refer to the multiple target wounds that can occur in a patient. As stated in the protocol, a non-inferiority margin will be incorporated into the analysis that will represent a 7-day advantage to the SOC group. This will be done by adding 7 days to the wound closure times in the SOC group. After that, the proportional hazards assumption will be checked in the same way as in the analysis of the timely eschar removal endpoint. I.e. a marginal cox regression model with a robust sandwich estimator (see below for further details) will be performed including the variables treatment, TW depth (on a wound level), %TBSA (on a wound level) and number of TWs (1, 2, ≥ 3) as well as a variable

representing the interaction between time since randomization and treatment group. If the coefficient for this time variable is non-significant at the 5% significance level, then the proportional hazards assumption will be considered appropriate. In this case we will use a marginal Cox regression analysis with a robust sandwich estimator. If not, then we will use an accelerated failure time (AFT) model with shared frailty. Note that this deviates from the previously planned parametric frailty model implemented in the SAS procedure PHREG. The latter one assumes proportional hazards and is therefore not suitable here.

Either method can be implemented in SAS (see [33] for details). The marginal Cox regression model is implemented in the PHREG procedure and the robust variance option is implemented by specifying the COVS(AGGREGATE) option. This induces the use of the robust variance method of Binder et. al. [34]. The accelerated failure time model with shared frailty will be implemented using the following SAS-code:

```
PROC NLIN DATA=burn_data;
BOUNDS gamma>0;
linp = b0 + b1*treatment_group + b2*spt + b3*dpt + b4*ft + b5*tbsa +
b6*number_tw2+ b7*number_tw3 + b8*center2 + b9*center3 + b10*center4 +
b11*center5 + z;
alpha = exp(-linp);
G_t = 1/(1+alpha*time**gamma);
g = alpha*gamma*time**gamma/(1+alpha*time**gamma)**2;
ll = (censor=0)*log(g) + (censor=1)*log(G_t);
model time~general(ll);
RANDOM z ~ normal(0,sigma) subject=subject_id;
RUN;
```

where subject_ID is a unique identification number for each patient, time is the time to wound closure on a wound level. Censor is a censoring indicator, treatment_group gives the treatment group, spt gives the % area SPT (on a wound level), dpt gives the % area DPT (on a wound level), ft gives the % area FT (on a wound level), TBSA gives the %TBSA (on a wound level), number_tw2 is an indicator variable for the subject having 2 target wounds (patient level), number_tw3 is an indicator variable for the subject having ≥ 3 target wounds (patient level), center2,...,center5 are indicator variables for the individual being in center group 2,...,5 (patient level) and burn_data is a SAS data set containing the required information.

The SAS code presented above calculates the treatment effect in an accelerated failure time model with shared frailty assuming a log-logistic distribution of the data. The commonly used Weibull-distribution is not applicable in this case, because the AFT model is equivalent to a proportional hazards model.

The presented methods include information on all the target wounds of each patient and account for any within-patient correlation. Missing information due to incomplete follow-up is incorporated naturally into such analyses as censored observations.

Kaplan-Meier curves will be presented graphically (see Figure 3) and in a table (see Table 8) to display the distribution of time to complete wound closure under the two treatments.

If any of the baseline factors, gender, age, or percent SPT area (the area of SPT as a percentage of the total area of all TWs, classified as <25% or ≥25%) are found to be significantly different between the treatment groups, then the factor will be included as an extra adjusting covariate in a supportive analysis of time to complete wound closure.

Furthermore, time to reach 100% wound closure will be analyzed as outlined above as an additional analysis.

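### The fallback code for time to wound closure names the wrong SAS procedure, carries one redundant parameter, and returns gamma times the log time ratio with no rule for rescaling or reporting it

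*SAP*

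**What the plan says.** SAP section 11.1.4.1 compares NexoBrid with SOC at wound level. The 7-day margin enters through the data: "This will be done by adding 7 days to the wound closure times in the SOC group". Next, "the proportional hazards assumption will be checked in the same way as in the analysis of the timely eschar removal endpoint". If the treatment-by-time term is not significant, a marginal Cox model is used. Otherwise the section prescribes an AFT model with shared frailty and prints its code.

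That code opens with "PROC NLIN DATA=burn_data", sets up "linp = b0 + b1*treatment_group + b2*spt + b3*dpt + b4*ft + b5*tbsa" plus dummies for number of wounds and center group and the patient effect, then has "alpha = exp(-linp)" and ends with "RANDOM z ~ normal(0,sigma) subject=subject_id". The covariates are described in the pattern "ft gives the % area FT (on a wound level), TBSA gives the %TBSA (on a wound level)". The text then states: "The SAS code presented above calculates the treatment effect in an accelerated failure time model with shared frailty", with a log-logistic distribution.

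The section assigns Kaplan-Meier output to Figure 3 and Table 8. It names no effect measure, no confidence interval and no table for the treatment effect.

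**The concern.** Section 6.4 binds the analysis to the SAP, so printed code matters. This code raises three problems.

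- **It does not run as printed.** RANDOM and a general log-likelihood belong to NLMIXED, not to NLIN.
- **One parameter is redundant.** The three depth areas together with an intercept and tbsa are linearly dependent, so the Hessian is singular.
- **The scale is not that of an AFT effect.** The only treatment parameter returned is b1, a frailty-conditional log odds ratio. The SAP leaves open whether b1, exp(b1) or b1/gamma is the reported effect. Reporting b1 or exp(b1) as the AFT effect would be wrong by a factor gamma on the log scale.

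The effect estimate and interval of a main safety endpoint are at stake. The same method also serves the per-protocol repeat, the 100% closure analysis, and the early- and late-grafted wound analyses.

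**Working it through.** The SAP gives no power or effect figure for this endpoint, so there is none to reproduce. The check covers the design matrix, the algebra, the size of the scale problem, and how often the fallback would be used. SAS was not run; the statement about NLIN rests on the syntax of the named procedure.

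**Redundant parameter.** Section 10.3.3.3.2 uses percent area per depth as a share of the target wound, and section 7.3.1 gives overall wound area as SPT + DPT + FT.

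- Read as shares, spt + dpt + ft = 100 for every wound, which duplicates b0.
- Read as %TBSA, spt + dpt + ft = tbsa, which duplicates b5.

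Simulated wounds gave 12 columns of rank 11 under both readings. In the 200-trial runs below, the smallest Hessian eigenvalue was at most 1.4e-10 as printed and had a median of 0.41–0.47 after dropping spt. Dropping spt moved the z value of b1 by at most 0.02. So b1 is estimable; what the software prints as its standard error depends on how it handles a singular Hessian.

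**Scale.** The code has S(t) = 1/(1 + exp(−linp)·t^gamma). The median solves t^gamma = exp(linp), so it is exp(linp/gamma). Raising linp by b1 multiplies the median by exp(b1/gamma). Hence log time ratio = b1/gamma, and b1 = gamma × log time ratio. For b1 = 0.6, exp(b1) = 1.82 whatever gamma is, while the time ratio is 1.49, 1.35, 1.22 and 1.13 for gamma = 1.5, 2, 3 and 5. (The printed g is t times the density; the extra factor contains no parameter and does no harm.)

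**Size.** The SAP gives no value of gamma, so 2, 3 and 4 are assumed, with an assumed true time ratio of 30/37 = 0.81 against SOC plus 7 days. Algebra gives exp(b1) = 0.81^gamma. If exp(b1) is read as a time ratio, the error on the log scale is (gamma − 1) × log(30/37) = −0.210 × (gamma − 1). Divided by the simulated standard error of b1, this gives the expected coverage.

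The simulation used 200 trials per gamma, 75 patients per arm, 1–3 wounds each (234–298 wounds), 5 center groups, frailty variance 1 on the linp scale, and censoring uniform over 67–167 days.

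| gamma | 2 | 3 | 4 |
|---|---|---|---|
| exp(b1) by algebra | 0.66 | 0.53 | 0.43 |
| exp(b1), simulated geometric mean | 0.64 | 0.52 | 0.41 |
| exp(b1/gamma), simulated | 0.80 | 0.81 | 0.81 |
| Median SE of b1 | 0.280 | 0.285 | 0.292 |
| Error / SE | 0.75 | 1.47 | 2.15 |
| Coverage of 0.81 by exp(b1) interval, expected | 88% | 69% | 42% |
| Same, simulated | 86% | 59% | 39% |
| Coverage by b1/gamma interval, simulated | 94% | 93% | 93% |

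A separate simulation gave 0.63, 0.53 and 0.44 for exp(b1), coverage of 85%, 64% and 40%, and 91–97% for b1/gamma.

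**Effect on the test.** Gamma is positive, so b1 = 0 exactly when the time ratio is 1. The likelihood-ratio statistics were identical. The Wald z for b1 and for b1/gamma differed by a median of 0.01, 0.04 and 0.07 (largest 0.50), and the 5% decision differed in 2 of 589 trials. Eleven of 600 trials with a near-singular Hessian even after dropping spt were left out of these z, coverage, mean and SE figures.

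**How often the fallback applies.** The 7 days are added before the proportional-hazards check. With equal raw times (log-logistic, median 30 days, shape 3, assumed), the SOC to NexoBrid hazard ratio after the shift is 0.09 at day 10, 0.51 at day 20 and 1.08 at day 60. In simulation (500 trials in each of 12 assumed settings per delay), the check was significant in:

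- 30–95% of trials with equal raw times (median of settings 62%);
- 14–49% if NexoBrid is 3.5 days slower (24%);
- 5–10% at the 7-day margin (7%).

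**The case against.** The strongest reply is that nothing inferential changes. The null, the direction and the likelihood-ratio test are the same on either scale, and the endpoint lies outside the efficacy hierarchy of section 11.1.8. This stands and limits the weight of the point.

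Second, the poor coverage arises only if someone labels exp(b1) a time ratio, which the SAP does not do. A log-logistic model is also a proportional-odds model, so b1 is a legitimate conditional log odds ratio. That is true, but the SAP presents the code as delivering the AFT treatment effect, and a reader would take that to be a time ratio. For the scar score in section 11.2.4.2, by contrast, the SAP says what the coefficient represents, which confidence bound is used and which table shows it.

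Third, NLIN is an obvious slip that stops at the first run, and the independent second implementation in section 6.4 should expose it. Agreed; but that repeat need not expose the scale if both statisticians report b1.

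Fourth, the missing results table affects the Cox branch as well, a generic shell (Table 7) exists, and the SAP cites a source for implementation details that is not at hand. These points explain the gap but do not correct the printed code.

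**Conclusion.** The concern holds on all three parts. As printed, the code names the wrong procedure, has one non-identified parameter, and returns gamma times the log time ratio with no rescaling.

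The consequence is limited to the reported effect and interval, and to whether a clean standard error is obtained; the non-inferiority decision is essentially unaffected. The size of the scale error is gamma itself on the log scale. The figures for exp(b1), coverage and fallback frequency rest on assumed gamma, frailty variance, closure times and censoring. The algebra and the rank deficiency need none of these assumptions.

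The correction should be made before the analysis because the fallback is not a remote branch when raw closure times are similar. Its use becomes uncommon as NexoBrid approaches the margin.

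**What to change.** In section 11.1.4.1:

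- Name PROC NLMIXED.
- Drop one of spt, dpt and ft.
- Either write alpha = exp(−gamma·linp), so that b1 is the log time ratio, or report b1/gamma with a delta-method interval.
- Name the table that carries this estimate and its confidence interval.
- State that the ratio compares NexoBrid with SOC plus 7 days, so that 1 marks the margin and not equality.

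As a clarification only, list the covariates of the final Cox model and use the same set in both branches. The list given for the proportional-hazards check omits center group. The eschar-removal model it refers to (section 11.1.3.2) includes center group, and so does the AFT code.

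The cost is a few lines of code and text. No new data are needed.

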11.1.4.2. Safety Endpoint: Cosmesis and function at 12 months from wound closure

Not applicable for this stage of analysis since the relevant information for all patients is not available yet. This endpoint will be analyzed in the second stage analysis (see 11.2.4.2).

11.1.4.3. Safety Endpoint: Cosmesis and function at 24 months from wound closure

Not applicable for this stage of analysis since the relevant information for all patients is not available yet. This endpoint will be analyzed in the third stage analysis (see 11.3.4.3).

11.1.4.4. Adverse Events

In this analysis, only the adverse events occurring in the acute phase (until the 3 months follow-up for each patient) will be analyzed.

All adverse events will be listed (see Table 14).

Adverse events are classified as being general, local – TW related or local – not TW related in the eCRF. Per each of these categories, the AEs will be listed as given in Table 9 and Table 10. The listing will be presented separately by:

- System organ class
- Preferred term
- Severity (mild / moderate / severe AEs)
- Relatedness (not related / remotely related / possibly related / probably related / related AEs)

- Time of onset (before start of treatment / during the treatment session / during the first week after treatment / during week 2 to week 4 after treatment / during week 5 to week 8 after treatment / more than 8 weeks after treatment)

SAEs will be analyzed in the same way as AEs.

11.1.4.5. *Vital Signs*

All vital signs (body temperature, heart rate, respiratory rate, systolic blood pressure, diastolic blood pressure) will be analyzed descriptively with number of subjects, number of missing values, mean, standard deviation, min, max, median and quartiles as shown in Table 4 and compared between groups with a one way analysis of variance. A graphical representation of the data will be done using histograms.

The analyses will be done for the vital signs assessments at screening, post eschar removal procedures, at the first 7 daily assessments as well as for the pre-post differences per procedure and the pre-post differences of the daily vital signs assessments described in Section 10.3.4.4 separately.

Furthermore, for the vital signs assessment at screening, post eschar removal procedures and at the first 7 daily assessments the information whether the overall vital signs assessment was normal, abnormal (NCS) or abnormal (CS) is given in the eCRF. These classifications will be analyzed separately for each time point of vital signs assessment by displaying counts and percentages by treatment group (see Table 5). The proportion of normal / abnormal (NCS) and abnormal (CS) assessments will be compared between treatment groups using a chi square test (or Fisher's exact test in case of small estimated cell counts). Bar plots of the proportions of patients with normal / abnormal (NCS) and abnormal (CS) assessments will be shown.

11.1.4.6. *Pain Assessment*

The pain assessment score will be analyzed descriptively with number of units, number of missing values, mean, standard deviation, min, max, median and quartiles as shown in Table 4 and compared between groups with a one way analysis of variance. A graphical representation of the data will be done using histograms. Furthermore, a plot of the mean pain (and the mean change in pain from baseline) over time will be presented.

The analyses will be done for the pain assessments at screening, pre and post eschar removal procedures, at the first 7 daily assessments as well as for the pre-post differences of the daily vital signs assessments (difference to baseline) described in Section 10.3.4.4 separately.

Furthermore, for the pain assessment at screening, pre and post eschar removal procedures and at the first 7 daily assessments the information whether the pain assessment was normal, abnormal (NCS) or abnormal (CS) is given in the eCRF. These classifications will be analyzed separately for each time point of vital signs assessment by displaying counts and percentages by treatment group (see Table 5). The proportion of normal / abnormal (NCS) and abnormal (CS) assessments will be compared between treatment groups using a chi square test (or Fisher's exact test in case of small estimated cell counts).

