In partial, mixed thickness, and intermediate depth wounds, and with difficult to diagnose depth “indeterminate” wounds, early surgical debridement will usually be avoided and a more conservative debridement approach using topical medications will be pursued. Such conservative non-surgical debridement lasts for days until the eschar decomposes or until a decision is taken to excise the offending, remaining eschar. The non-surgical debridement process involves the combined activity of topical medications, contaminant microorganisms, autolytic tissue processes and the inflammatory process with frequent dressing changes, showering, mechanical scraping of loose debris etc. The infectious-inflammatory processes are slow (lasting between 10-14 days) and may involve significant systemic and local complications. Using topical anti-bacterial or anti-inflammatory medicaments may reduce the infectious-inflammatory processes but will also delay eschar separation (sloughing). Locally, all these processes prolong the removal of the eschar and lead to additional tissue damage due to the death of the Zones of Stasis and Hyperemia which deepen, transforming partial thickness damage into a full thickness injury. The long debridement time with sustained inflammatory processes can lead to the formation of granulation tissue that will develop into heavy scars.

This excerpt of literature emphasizes that timely eschar removal is, for the last 40 years, the goal of burn wound care initiation. Physicians today are forced to choose between or combine two sub optimal alternatives of eschar removal; (i) the fast and efficient surgery (TE&STSG) with its diagnosis-dependent often prolonged initiation, non-selective, traumatic and demanding results or (ii) the inefficient non-surgical prolonged debridement means with their associated sequelae. The lack of fast and effective non-surgical eschar removal means has left surgery as the available SOC for deep burns.

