7.1.2. Intended dosage and duration of treatment

7.1.2.1. *NexoBrid*

Two grams or five grams of NexoBrid sterile powder are mixed in 20 grams or 50 grams of sterile Gel Vehicle (ratio of 1:10), respectively to obtain sterile NexoBrid Gel. NexoBrid Gel is applied to the burn wound at a dose of 2 g NexoBrid sterile powder mixed with 20g sterile Gel Vehicle per 1% of TBSA (~ surface of an adult palm) for four hours (or 5 g NexoBrid sterile powder mixed with 50g sterile Gel Vehicle per 2.5% of TBSA). The NexoBrid powder and the Gel Vehicle are to be mixed at the patient bedside ≤ 15 min prior to use.

NexoBrid should not be applied to more than 15% TBSA in one session.

NexoBrid may be applied for a second time to the same burn area, if eschar removal from the target wound after the first application is not complete but at least 50% of the eschar was removed during the first application. NexoBrid may only be applied twice to the same burn wound area.

7.1.2.2. *Gel Vehicle*

Twenty (20) grams or 50 grams of sterile Gel Vehicle will be applied on the burn skin. Gel Vehicle is applied to the burn wound at a dose of 20 grams sterile Gel per 1% of TBSA (~ surface of an adult palm) or 50 grams per 2.5% TBSA for four hours.

Gel Vehicle should not be applied to more than 15% TBSA in one session.

Gel Vehicle may be applied for a second time to the same burn area, if eschar removal from the target wound after the first application is not complete but at least 50% of the eschar was removed during the first application. The Gel Vehicle may only be applied twice to the same burn wound area.

7.1.2.3. *Standard of Care*

No more information on intended dosage or duration of treatment was specified in the protocol for the Standard of Care arm than that already given in Section 7.1.1.2.

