7.2. Trial schedule

The healing and care of the burn wound may be divided into the three distinctive phases:

1. Eschar removal treatment phase (until complete eschar removal)
2. Wound management (until complete wound closure)
3. Scar modulation and maturation

These phases are common to the care of all wounds and are well defined in acute wounds such as burns.

In this study, these phases and their treatment strategy are equal for all arms, NexoBrid, SOC, and Gel Vehicle, following the ABA white paper recommendations [24].

The total duration of the study treatment and follow up period of each participating subject is expected to be 25 months: following the Eschar removal procedure, each subject will be followed up weekly (Weeks 1, 2, 3 and 4 etc.) until complete wound closure is achieved and 2 weeks later for wound closure confirmation, for each of the subject's TWs. Long-term follow-up visits will be performed at 1, 3, 6, 12, 18 and 24 months post last wound closure confirmation visit (for details see Table 1).

Table 1: Treatment flow chart - all arms³

If applicable
 * Weekly FU assessments will be performed every 7± 2 days from start of treatment until complete wound closure. Long-term FU will be performed 1,3,6,12,18 and 24 M after last wound closure confirmation.
 **First treatment session will include any procedure for eschar removal: the NexoBrid®/Gel Vehicle/Surgical or non-surgical procedure, as per randomization arm
 ** Procedure can be either surgical or non-surgical. A whole period of continuous dressing changes (from first coverage application to last coverage application) is considered as one non-surgical procedure, assessments should not be repeated for each dressing change; Pre procedures assessments refer only to surgical procedures. Post procedures assessments refer to any surgical procedures and for non-surgical procedure only if it is the last procedure

Parameter	Screening tests	Baseline within 1 h Pre First treatment session - All arms	Topical arms (NexoBrid or Gel Vehicle): (refer to first and second application). S=Soaking, R=Removal	SOC procedures** (including additional procedures in the topical arms)	Daily assessments	Management & Re-admissions ⁴ - surgical procedures assessment	Wound	HD or premature discontinuation visit	Weekly FU*	Long-Term FU (1, 3, 6,12,18 & 24 months)*
Inform Consent signing	X									
Medical history	X									
Burn History ⁵	X									
ConMeds & AEs	X	X	X	X	X	X	X	X	X	X

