10.3.2. Primary Endpoint: Incidence of complete eschar removal in the topical arms

Information on whether complete eschar removal was obtained after the application of NexoBrid or Gel vehicle per target wound will be combined to a single binary variable (yes/no) indicating whether complete eschar removal was achieved for all target wounds of a patient at the end of the eschar removal treatment (after the 2 hrs soaking). The eschar removal treatment may contain one or two topical removal procedures. Complete eschar removal is judged after the last topical procedure in a patient.

Furthermore, for all patients with at least one early grafted target wound (for definition see Appendix 13.1.1), a binary (yes/no) variable will be computed indicating whether complete eschar removal has been achieved in all early grafted wounds of the patient at the end of the eschar removal treatment (after the 2 hrs soaking).

Additionally, for all patients with at least one late grafted target wound (for definition see Appendix 13.1.1), a binary (yes/no) variable will be computed indicating whether complete eschar removal has been achieved in all late grafted wounds of the patient at the end of the eschar removal treatment (after the 2 hrs soaking).

Furthermore, for patients who had at least one target wound that is found, at least partially, in the anatomical area of the hand, a binary (yes/no) variable will be computed, indicating whether complete eschar removal has been achieved in all target wound that are found, at least partially, in the anatomical area of the hand.

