- Time of onset (before treatment / during the treatment session / during the first week after treatment / during week 2 to week 4 after treatment / during week 5 to week 8 after treatment / more than 8 weeks after treatment)

For each of the tree stages of analysis (see Section 11 for details), the safety data gathered in that stage will be analyzed separately. That is, in the acute stage analysis, all AEs reported until the 3 months follow-up will be analyzed. In the second stage analysis (12 months follow-up), all AEs reported between the 3 months follow-up and the 12 months follow-up (including AEs from the first stage that are still ongoing) will be analyzed. Analogously, in the third stage analysis (24 months follow-up), all AEs reported between 12 months follow-up and the 24 months follow-up (including AEs from the first or second stage that are still ongoing) will be analyzed.

Vital signs

Body temperatures given in °F will be transformed to °C using the following formula:

$$Temperature[^\circ C] = \frac{5}{9}(Temperature[^\circ F] - 32)$$

Differences in the vital signs assessments (body temperature, heart rate, respiratory rate, systolic blood pressure, diastolic blood pressure) between daily visits will be calculated by

$$Diff_d = VS_{d-1} - VS_d$$

where VS_d is the vital sign assessment at day d (daily follow-up) and d is varied from 2 to 7. Furthermore, pre-post differences for vital signs assessments per procedure will be calculated in the same way, using the screening assessment as pre first procedure and the post first procedure measurement as pre second procedure measurement if needed.

Pain assessment

For each eschar removal procedure and each daily follow-up pain assessment the change in pain from baseline will be calculated as

$$Diff_d = Pain_{Base} - Pain_d$$

where $Pain_d$ is the pain assessment at the respective time point. For the calculation of the difference in pain for the eschar removal procedures the pain assessment post that procedure will be used.

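### The adverse-event onset bins have no defined anchor, so the onset table is not comparable between NexoBrid and dressing-treated SOC patients (minor)

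*SAP*

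**What the plan says.** Section 11.1.4.4 breaks down first-stage AEs, and SAEs in the same way, by time of onset: "Time of onset (before start of treatment / during the treatment session / during the first week after treatment", followed by weeks 2 to 4, weeks 5 to 8 and beyond 8 weeks after treatment. Section 10.3.4.4 has nearly the same list for systemic and for local events: "Time of onset (before treatment / during the treatment session / during the first week after treatment". Table shells 9 and 10 in section 13.2 set SOC, NexoBrid and Gel Vehicle side by side. Neither section says when a session starts or ends, or from which moment time after treatment is counted.

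The nearest thing to a definition is the legend to Table 1 in section 7.2. It says "First treatment session will include any procedure for eschar removal", whether topical, surgical or non-surgical, according to the randomized arm. It adds: "A whole period of continuous dressing changes (from first coverage application to last coverage application) is considered as one non-surgical procedure".

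For NexoBrid, section 7.1.2 gives the dose per 1% TBSA ("surface of an adult palm) for four hours") and states that "NexoBrid may only be applied twice to the same burn wound area". Section 10.3.2 places the primary assessment "at the end of the eschar removal treatment (after the 2 hrs soaking"). Section 7.1.1.2 lets SOC be surgical, non-surgical or both, and sets no duration.

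**The concern.** The third study objective (section 2.2) is safety of NexoBrid against SOC, so readers will compare the onset table across these two arms. That comparison needs each row to cover the same stretch of time in each arm. Here the row boundaries depend on session length, which is fixed at hours in the topical arms but may run to days for a SOC patient treated with dressings.

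Two arms with identical true event rates could then show different onset profiles: few NexoBrid events during the session and many in the first week, with the reverse in dressing-treated SOC. A reader could take this for an early safety signal, or for reassurance about the treatment period, when it comes only from how the rows are cut.

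**Working it through.** The plan gives no figure to reproduce here. The check is to place the bins on one clock, in days from the start of the first session, under each reading of the text.

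**Inputs**
- Topical session: 4 h application (7.1.2) + 2 h soak (10.3.2) = 6 h, so L = 6/24 = 0.25 day.
- Non-surgical SOC session: first to last coverage (Table 1 legend). No length is given. L = 1, 3 and 7 days are assumed values. L = 10 and 14 days come from the background section ("The infectious-inflammatory processes are slow (lasting between 10-14 days"), which describes conservative care in general and not this trial.

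**Reading A: weeks counted from the end of the session.** First week = [L, L+7]; weeks 2 to 4 = [L+7, L+28]. Days shared with the topical first week (0.25 to 7.25) = max(0, 7.25 − L).

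**Reading B: weeks counted from the start, with the session bin taking precedence.** Days left in the first week = max(0, 7 − L). Any excess of L over 7 is taken from weeks 2 to 4.

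| Session length L (days) | A: first week | A: days shared with topical | A: weeks 2 to 4 | B: first-week days left |
|---|---|---|---|---|
| 0.25 (topical) | 0.25–7.25 | 7 | 7.25–28.25 | 6.75 |
| 1 | 1–8 | 6.25 | 8–29 | 6 |
| 3 | 3–10 | 4.25 | 10–31 | 4 |
| 7 | 7–14 | 0.25 | 14–35 | 0 |
| 10 | 10–17 | 0 | 17–38 | 0 (3 more from weeks 2–4) |
| 14 | 14–21 | 0 | 21–42 | 0 (7 more from weeks 2–4) |

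If the session bin does not take precedence under reading B, an event on day 2 of a 3-day dressing period belongs to both the session and the first week, so the rows are not mutually exclusive.

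**Topical patients are ambiguous too.** With two applications, if weeks run from the end of the first session, an event during the second falls in two bins. If weeks run from the end of all eschar removal, an event between the two falls in none. Table 1 also provides for SOC procedures after topical treatment, and the text does not say whether these extend the treatment.

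**Illustration under reading A.** Assume the same event hazard in both arms, with exponentially distributed onset of mean m days. The share in [a, b] is exp(−a/m) − exp(−b/m). The means are assumptions, not document figures.

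| L (days) | Session, m = 7 | First week, m = 7 | Session, m = 14 | First week, m = 14 |
|---|---|---|---|---|
| 0.25 | 3.5% | 61.0% | 1.8% | 38.7% |
| 3 | 34.9% | 41.2% | 19.3% | 31.8% |
| 10 | 76.0% | 15.1% | 51.0% | 19.3% |
| 14 | 86.5% | 8.6% | 63.2% | 14.5% |

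For example, with L = 3 and m = 7, session = 1 − exp(−3/7) = 34.9% and first week = exp(−3/7) − exp(−10/7) = 41.2%. These shares apply to a dressing-treated SOC patient, not to the SOC arm as a whole. A SOC patient whose session lasts one day has bin edges only 1 − 0.25 = 0.75 day later than a topical patient.

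**The case against.** The strongest objection is that the plan does not say weeks run from the end of the session, and elsewhere it points the other way. Table 1 counts weekly visits from the start of treatment, and 10.3.4.4 describes the post-treatment PTT/INR visits as 24 h and 48 h after debridement starts. On that reading the later weekly bins align: a day-16 event falls in weeks 2 to 4 in every arm. This stands, and it rules out saying that the weekly bins are shown to differ. It does not rescue the table, because the session bin still differs in length and overlaps or depletes the first week.

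Second, the one-procedure rule in the Table 1 legend is there to avoid repeating assessments at each dressing change. Nothing ties it to AE onset, and where the SAP means the whole eschar removal period it says so (blood transfusions, 11.1.4.11). This is fair. The legend permits the long session without compelling it, but no competing definition is offered.

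Third, a reader might infer an arm-level figure. With 60% of SOC patients expected to need excision (9.2), 40% would not. Spreading events evenly over 21 days would then put 0.40 × 10/21 = 19% to 0.40 × 14/21 = 27% of SOC events in the session bin, against 6/504 = 1% for NexoBrid. The documents do not support this. The 10 to 14 days is background text. Every SOC patient without excision is given the full period, although the plan's own event proportion for complete eschar removal in SOC is 0.728 (9.3). On the NexoBrid side, second applications and rescue procedures are ignored, although complete removal by topical treatment is anticipated in only 0.5665 (9.1.1). The constant rate is assumed.

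Finally, onset is one of five descriptive breakdowns and has no test. Table 14 lists start dates, so timing can be recovered. This stands and sets the severity.

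**Conclusion.** The point holds as a minor one. The onset bins in 10.3.4.4 and 11.1.4.4 lack an anchor, and neither a start nor an end anchor makes the present list both comparable across arms and mutually exclusive when SOC is given as a run of dressings. The affected output is the descriptive NexoBrid-versus-SOC onset table, for dressing-treated SOC patients. Onset in topical patients with a second application or rescue procedures is ambiguous as well.

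The size cannot be fixed from the plan. Under the end-of-session reading, the shared part of the first week falls from 6.25 days at a 1-day dressing period to 4.25 at 3 days and to zero from 7.25 days upward. The 10 to 14 days in the background is only an upper illustration. SOC patients whose session lasts no more than a day are barely shifted.

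It would go too far to conclude that the safety comparison as a whole is biased. Total counts to the 3-month follow-up and the breakdowns by system organ class, preferred term, severity and relatedness do not depend on these bins, and no efficacy or non-inferiority conclusion uses them.

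**What to change.** In 10.3.4.4 and 11.1.4.4, anchor the onset bins in every arm to one time zero, either the start of the first treatment session or randomization, and make them mutually exclusive: before time zero; day 1; days 2 to 7; weeks 2 to 4; weeks 5 to 8; after week 8. Show onset during topical application and soaking as a separate row for the topical arms only, counted over every session and outside the mutually exclusive list.

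The cost is SAP wording and table shells. AE onset date and time are already recorded (7.3.3.4), so no new data are needed. The downside is that SOC no longer has a row for events during the session. Merely defining the two terms would remove the ambiguity but would leave session lengths, and hence the early rows, different between arms.
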